Microbiome study (26) suggested that patients with Th2-low asthma, the same group that responded in the AZISAST study, have a higher microbial burden than patients with the Th2-high phenotype. The AMAZES trial, in contrast, did not distinguish a difference in Th2-high versus Th2-low asthma in the efficacy of azithromycin on exacerbations. Differences in bacterial biomass or composition, all of which may reflect a dysbiotic microbiome, may be one key factor: azithromycin may work in these patients. None of the above-cited studies examined the microbiome, and so a key link to understand how macrolides might benefit patients with poorly-controlled asthma is missing. Neutrophilic asthma, one key Th2-low subtype, is associated with increased bacterial load and pathogens (identified by culture) such as *Hemophilus*, *Pseudomonas*, and *Moraxella* (48). Identifying the correct patient group may be the key to resolving the conflict of whether azithromycin is useful in asthma.

Why would a new study succeed where past, non-selective studies have failed? We hypothesize that in the right asthma phenotype – neutrophil dominant, Th2-low – modifying the dysbiotic microbiome in turn improves clinical control. Our trial will focus on the relation of asthma control to changes in the microbiome induced by azithromycin and understanding the influence of Th2-based phenotypes on this response. By careful examination of the dysbiotic microbiome, careful focus on Th2-low asthmatic patients, and focusing on patients with poor control in which the potential signal is substantial, we will answer the question definitively.

Purpose

The purpose of this protocol is to perform a short-term pilot study so as to acquire data critical to the proper design of a full-scale RCT. The primary objectives of the pilot study are to:

- a) Estimate variability of microbiome composition and diversity over time in control and asthmatic subjects to provide a baseline for the future RCT
- b) Estimate the response of the airway microbiome to azithromycin over time, so that we can generate appropriate power calculations and sample size estimates for the future RCT
- c) Refine our microbial informatics pipeline for the future RCT
- d) Refine our sputum gene expression and cytokine array testing
- e) Test the feasibility of our intervention in a small cohort of subjects with poorly-controlled asthma

Study Design

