This pilot protocol examines the change in the airway microbiome after azithromycin over an 8 week period. 40 subjects with poorly controlled asthma and 10 control subjects with no known lung disease will undergo clinical data collection including ACT score, lung function, exhaled nitric oxide (FeNO), methacholine challenge, and induced sputum and blood collection. Participants with asthma then are randomized 1:1 to receive azithromycin, 250 mg, or placebo, daily for 8 weeks. Clinical parameters including ACT, oral wash, adherence, side-effect profile, spirometry, and biological specimens (sputum, blood, FeNO) are collected again at 4 and 8 weeks. Control subjects undergo the same measurements, but do not receive any intervention.

Schedule of Events

	Asthma (A) or Control (C)	Visit 1/Week 0 (Screening) (+/- 3 days)	Visit 2/Week 4 (+/- 3 days)	Week 6 (+/- 3 days)	Visit 3/Week 8 (+/- 3 days)	Week 10 (+/- 3 days)	Visit 4/Week 12 (+/- 3 days)	Week 14 (+/- 3 days)
Informed Consent	A,C	X						
Site Visit	A,C	X	X		X		X	
Phone Call	A			X		X		X
Confirmation of Eligibility	A,C	X	X					
Randomization	A		X					
Drug Dispensation	A	X ^{1,2}	X ^{1,2,3}		X ^{1,2,3}		X ^{1,2}	
Demographics	A,C	X						
Medical History Review	A,C	X						
Asthma History	A	X						
Smoking History	A,C	X						
Concomitant Medication Review	A,C	X	X		X		X	
Physical Exam/Vital Signs	A,C	X	X		X		X	
Asthma Control Test	A	X						
Demographics Questionnaire	A,C	X						
Family History Questionnaire	A,C	X						
Work Exposures Questionnaire	A,C	X						
Home Exposures Questionnaire	A,C	X						
Physical Activity Questionnaire	A,C	X						
Secondhand Smoke Exposure Questionnaire	A,C	X						
Peak Flow Meter Readings ⁵	A	X	X	X	X	X	X	X
Electronic Diary ⁴	A	X	X	X	X	X	X	X
ECG	A,C	X	X		X		X	
Spirometry with Reversibility ⁶	A,C	X	X		X		X	
Exhaled NO	A,C	X	X		X		X	
Urine Pregnancy Test ⁷	A,C	X						
Methacholine Challenge ⁸	A,C	X	X		X		X	
Sputum Induction	A,C	X	X		X		X	
Oral Wash	A,C	X	X		X		X	
Complete Blood Count with Platelet Count and Differential Blood Sample	A,C	X			X			
Serum IgE Blood Sample	A,C	X						
RAST Blood Analysis	A,C	X						
Research Blood Samples	A,C	X			X			
Adverse Events Review	A,C		X	X	X	X	X	X
Compliance/Adherence to Diary and Study Drugs	A	X	X	X	X	X	X	X

1. Dispensation of albuterol to asthmatic subjects (if required at Visit 2 and Visit 3)
2. Dispensation of ICS/LABA to asthmatic subjects
3. Dispensation of azithromycin/placebo to asthmatic subjects

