We will limit sources of and account for potential contamination in our data pipeline, such as in reagents and kits (60,61) and in processing MiSeq-generated sequences (62,63). We will handle contamination issues by: 1) eliminating OTUs that are substantially increased when total 16S is low, 2) randomize samples to different extraction kits and re-run with a different lot-numbered kit to confirm findings, 3) do phenol-chloroform extractions instead of relying exclusively on kits, 4) maintain consistency in kits and lots for each analysis, and 5) cycle bar codes between runs.

We will use FASTX-Toolkit for quality trimming of Illumina files. The QIIME pipeline is used for primer trimming, chimera checking and sequence alignment, taxonomic classification and calculation of α and β diversity indices, and generation of rarefaction curves. We construct an abundance matrix of reference OTUs and phylogenetic trees derived from the GreenGenes reference set (64). We will employ a suite of multivariate statistical tools to compare amplicon data between and within sample types by canonical correlation analysis, regression profiling, and visualization (e.g. non-metric multi-dimensional scaling [NMDS], Principal Coordinates of Analysis, and Principal Components Analysis). We will also look at the species diversity of each sample and observe if there is any variation between the cohorts. In addition, we will use nonparametric statistics (ANOSIM, ADONIS, ANOVAR, PERMANOVA, etc.) to determine the statistical significance of participant factors. Significance of differences in relative percentage and diversity indices between groups will be calculated using Student's t-test. The Pearson correlation coefficient will be used to assess correlations among continuous variables.

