Microbial bioinformatics. We will employ a suite of multivariate statistical techniques, network modeling and machine learning approaches to characterize the composition and structure of the microbial community between and within the normal subjects and asthma experimental arms, and determine microbial biomarkers that correlate with ACT score, albuterol use, changes in FEV1, and markers of airway inflammation. All amplicon sequencing data will be quality filtered and de-multiplexed and then subjected to de novo operational taxonomic unit (OTU) picking, and sub-OTU characterization using DeBlur (<https://github.com/biocore/deblur>.) Microbial diversity will be summarized using Chao1 estimator and Shannon index, and association with clinical and immune variables will be tested by regression analysis and generalized linear modeling. UniFrac distances (between-sample beta diversity) will be used to visualize and test the overall microbiota structure difference between study arms using multivariate methods such as principal coordinate analysis (PCoA) and permutational multivariate analysis of variance (PERMANOVA). DESeq2, which allows correction for multiple testing, will be used to perform differential abundance analysis to identify clinically relevant taxa (65). Based on these results, logit models will be generated using dichotomized clinical and immune variables as outcomes, and the microbiome data as independent variables. Variable selection methods will be integrated to avoid over-fitting. Since we expect that the number of genera will be approximately equal to 300, a dimension reduction will be performed so that efficient statistical inference can be conducted, using either the LASSO (66) or thresholding (67) methods within the context of high-dimensional inference for generalized linear mixed effects models. Classification performance will be evaluated using ROC curve and the 0.632+ bootstrap method (68). The machine learning approach, Random Forest, will also be applied to determine whether the microbiome is predictive of clinical outcomes (69). We will also examine whether there are natural grouping patterns in the microbial community data and, if so, how these grouping patterns relate to asthma phenotypes. To do this, we will compute Bray-Curtis dissimilarity measures between subjects and perform hierarchical cluster analysis and nonmetric multidimensional scaling to visualize if the groupings determined by the hierarchical clustering algorithm relate to asthma phenotypes. We will also fit multivariate analysis of variance (70) and ordination models for the relative abundance of the microbiome response against the treatment and time effects using the R package vegan (71).

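### Comparisons of the 10 controls with the asthma subjects should not rest on a pooled-variance t-test, unadjusted PERMANOVA or ANOSIM, because unequal spread would distort their error rates

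*Combined protocol and SAP*

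**What the plan says.** The group sizes are in the Study Design section: "40 subjects with poorly controlled asthma and 10 control subjects with no known lung disease will undergo clinical data collection". Then "Participants with asthma then are randomized 1:1 to receive azithromycin, 250 mg, or placebo, daily for 8 weeks", which makes two asthma arms of 20. For the controls, "Control subjects undergo the same measurements, but do not receive any intervention".

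Under Statistical analysis, the Initial microbiome analysis text says "We will also look at the species diversity of each sample and observe if there is any variation between the cohorts". It adds that "we will use nonparametric statistics (ANOSIM, ADONIS, ANOVAR, PERMANOVA, etc.) to determine the statistical significance of participant factors", and then: "Significance of differences in relative percentage and diversity indices between groups will be calculated using Student's t-test". The Microbial bioinformatics text sets out to characterise the "composition and structure of the microbial community between and within the normal subjects and asthma experimental arms".

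No unequal-variance t-test, variance check or dispersion test is named, and no allowance is made for unequal group sizes. The only SD given (1.8, in Power calculations) is for asthma patients on inhaled corticosteroid. There is none for controls.

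**The concern.** Student's t-test pools the two group variances, weighting each by its degrees of freedom. When the groups are equal in size this does little harm. When one is four times the other, the pooled variance is essentially that of the larger group, while the uncertainty of the difference comes mainly from the smaller group. If controls vary more than asthma subjects, the standard error is too small and false differences appear. If asthma subjects vary more, the standard error is too large and real differences are missed. PERMANOVA's pseudo-F has the same structure.

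Nothing in the documents supports assuming equal spread. The hypothesis of a dysbiotic microbiome in asthma gives some reason to expect the groups to differ in spread. At stake is how far the p-values and intervals for the asthma-control comparison can be trusted.

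**Working it through.** **Inputs from the documents.** 10 controls, 40 asthma subjects, 1:1 randomisation (so 20 per arm). Two-sided 5% is stated in Power calculations for the paired analysis and is used here as the nominal level. **Assumed:** the control:asthma SD ratio, taken from 0.5 to 2.

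**The plan's own figure.** No power or error rate is given for control v asthma. The one stated calculation is paired, with n = 20 and SD 1.8. The SD of change is 1.8 × √(2(1−ρ)), which is 1.39 at ρ = 0.7 and 1.80 at ρ = 0.5. A paired t-test with 80% power then detects 0.92 and 1.19 (stated: 0.9 and 1.2). The 95% half-widths are 2.093 × 1.39/√20 = 0.65 and 2.093 × 1.80/√20 = 0.84 (stated: 0.7 and 0.84). These reproduce and are not in question.

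**Why the pooled test goes wrong.** The true variance of the difference is σc²/nc + σa²/na. The pooled test uses, on average, [((nc−1)σc² + (na−1)σa²)/(nc+na−2)] × (1/nc + 1/na).

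- 10 v 40, control SD 2, asthma SD 1: true 4/10 + 1/40 = 0.425; used (36 + 39)/48 × 0.125 = 0.195. The standard error is too small by a factor √(0.425/0.195) ≈ 1.48.
- 10 v 40, control SD 1, asthma SD 2: true 1/10 + 4/40 = 0.200; used (9 + 156)/48 × 0.125 = 0.430. The standard error is too large; true over used is √(0.200/0.430) ≈ 0.68.
- 20 v 20: the two expressions are identical at any ratio.

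**Simulated type I error of Student's test** (nominal 5%, normal data, 200,000 data sets per setting):

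| Control:asthma SD | 10 v 40 | 10 v 20 |
|---|---|---|
| 0.5 | 0.5% | 1.9% |
| 0.67 | 1.4% | 2.7% |
| 0.8 | 2.5% | 3.6% |
| 1.25 | 8.6% | 6.8% |
| 1.5 | 12.2% | 8.6% |
| 2 | 18.1% | 11.5% (repeat runs 11.2-11.3%) |

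At 10 v 40 with equal SDs Student's test gives 4.9%. Welch's test gives 5.0-5.1% at 10 v 40 throughout. At 20 v 20 Student's test stays at 5.0-5.5%.

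**Power.** With asthma SD twice control SD and a true difference of 1.25 control SDs at 10 v 40, Student's test has 45% power and Welch's 77%. With equal SDs and a difference of 0.8 SD, Student's has 60% and Welch's 56%.

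**PERMANOVA, 10 v 40** (Euclidean distance, equal centroids, 1,000 data sets, 199 permutations). The pseudo-F is d²/[s²pooled(1/nc + 1/na)], with d the distance between centroids. The Welch-type statistic is d²/(sc²/nc + sa²/na).

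| Control:asthma SD | PERMANOVA, 3 dimensions | PERMANOVA, 20 dimensions |
|---|---|---|
| 0.5 | 0.1% | 0.0% |
| 0.67 | 0.7% | 0.0% |
| 0.8 | 2.1% | 0.5% |
| 1 | 5.7% | 5.5% |
| 1.25 | 10.5% | 23.7% |
| 1.5 | 16.8% | 46.0% |
| 2 | 29.4% | 74.5% |

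Two smaller 10-dimension runs gave 50% and 53% at ratio 2. The Welch-type permutation test gave 4.2-6.2% over all the settings in the table (Monte Carlo error about 0.7 points).

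**ANOSIM** (20 dimensions, equal centroids). At 10 v 40 it rejects 98-100% of the time when controls are more variable by 1.25 to 2, and 0% when asthma subjects are. At 20 v 20 it still rejects 34-100%, so imbalance is not the sole cause.

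**Limit of Welch.** For identical lognormal distributions (log-SD 1) at 10 v 40, plain Welch gives 8.2-8.5% and Student's 4.5-4.8%. With control SD 1.5 times, Welch gives 12.0% and Student's 10.8%; at twice, 13.9% and 18.6%.

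**The case against.** **No sentence assigns these tests to 10 v 40.** The t-test sentence says only groups, and participant factors is unspecific. The UniFrac PERMANOVA is worded for study arms. The later list of planned contrasts covers pre- to post-azithromycin and azithromycin v placebo, without controls. This stands as a limit: the 10 v 40 use is inferred from the reference to cohorts beside the t-test sentence, and from the normal subjects named under Microbial bioinformatics. The inference is reasonable, because no other two-group test is named for control-asthma differences in these measures.

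**A reader might infer that primary objective (a) is compromised.** The documents do not support that. The objective is "Estimate variability of microbiome composition and diversity over time in control and asthmatic subjects to provide a baseline for the future RCT", which is estimation of within-subject variability over time in each group, not a test of asthma against control means. The link is indirect: with within-subject correlation 0.5 or 0.7, doubling one group's within-subject SD raises its total SD by √(0.5 + 0.5 × 4) = 1.58 or √(0.7 + 0.3 × 4) = 1.38.

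**A reader might also infer that the treatment comparisons are at risk.** The randomised t-tests, including that of the primary ACT outcome, compare 20 with 20 and hold their level.

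**Other analyses are planned, and the protocol calls itself exploratory.** Mixed models, regression of diversity, DESeq2 and Poisson models are all listed, and no decision rests on a control-asthma p-value. This stands and limits the weight of the point.

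**The direction that dysbiosis suggests, asthma more variable, makes the tests conservative.** True, but the price is power, as the 45% v 77% shows.

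**Welch is not a universal cure.** Correct. Relative percentages are bounded at zero and may well be skewed, and there plain Welch can be worse than Student's. The remedy has to differ by type of measure.

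**Conclusion.** The point holds as a cheap improvement to an exploratory, non-randomised contrast. If the named tests are applied to controls v asthma subjects, their error rates depend on a spread ratio that the documents do not give. At 10 v 40 the distortion is visible at a ratio of 1.25 (8.6% or 2.5% for Student's test) and serious at 1.5 or more. At 10 v 20 it is milder.

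The figures assume normal data and SD ratios from 0.5 to 2. The PERMANOVA figures also assume Euclidean distance and vary strongly with dimension, so they show direction and order of size; they do not predict results for UniFrac or Bray-Curtis distances. If the spreads are in fact alike, the planned t-test and PERMANOVA keep about their nominal level.

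**What to change.** In the Initial microbiome analysis and Microbial bioinformatics text, for every comparison that includes controls:

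- State which groups are compared, and whether the asthma arms are pooled.
- Use Welch's t-test and interval for near-symmetric diversity indices such as Shannon.
- For relative percentages, use Welch on a suitable transformed scale (log or centred log-ratio, with a stated rule for zeros) or a studentised permutation test. A transformed scale compares a different summary from the raw mean percentage, so say which is meant.
- Report a dispersion test (betadisper/PERMDISP) beside each control-asthma PERMANOVA, and use a Welch-type distance permutation test for that contrast.
- Do not rely on ANOSIM as evidence of a difference in composition. It responds to spread even in balanced groups, so the same caution applies to the randomised arms.

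This needs no new data or visits. The cost is revised wording, a little more code, and a few points of power if the variances are equal (56% v 60% in the example above).

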For the COMPEX scores, we will determine the time to deterioration as defined in Fuhlbrigge et al (2017). This criteria defines a “diary event” as reaching a predefined change from baseline (threshold) for at least 2 consecutive days, or deterioration in all six variables comprising the COMPEX score over at least a 5-day period plus at least one variable reaching a threshold criterion for at least 2 consecutive days. A “CompEx event” is then defined as the first occurrence of either a diary event or a severe asthma exacerbation (deterioration of asthma leading to oral corticosteroid use, emergency room admission, or hospital admission). Patients who do not experience a CompEx event will be censored as of the last negative assessment. The time from baseline to a CompEx event in days will be compared in the two treatment arms using a logrank test.

Data analysis will be performed using R and STATA software. Linear mixed effects models will be fit for continuous longitudinal outcomes and ordinal, logit, and Poisson mixed effects models will be employed for ordinal, binary, and count responses, respectively (59).

Initial microbiome analysis. Microbiome analysis is done in collaboration with [name], who is Director of The Microbiome Center at the University of Chicago, which houses an advanced sample processing and sequencing core. Samples are partitioned into two aliquots: one for PCR amplification and analysis of the 16S rRNA V4-V5 hypervariable region using amplicon sequencing. We will independently do qPCR of total 16S rRNA of each sputum, oral and nasal sample to determine total load. We will use the Illumina MiSeq platform and barcoded primers to sequence PCR-libraries, and always include non-template and blank controls. The remarkable simplicity of airway microbiota allows a high level of multiplexing (>300 samples per MiSeq flow cell) and ensures 99.99% sequencing coverage after 10,000 reads.

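### Taxa-based logit models dichotomize outcomes that appear to be numeric, with no cut-points or reason given; under a normal model this loses at least about 36% of the information

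*Combined protocol and SAP*

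**What the plan says.** The Microbial bioinformatics paragraph sets the aim: to "determine microbial biomarkers that correlate with ACT score, albuterol use, changes in FEV1, and markers of airway inflammation". After a differential-abundance step, it states that "logit models will be generated using dichotomized clinical and immune variables as outcomes", and that the microbiome data enter as independent variables. Because "we expect that the number of genera will be approximately equal to 300", dimension is reduced by LASSO or thresholding, which the plan places within generalized linear mixed models. Classification is judged by ROC curve and the 0.632+ bootstrap. The sentence on dichotomizing names no variable, and no cut-point or rationale appears anywhere in the document.

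The sample, from Study Design, is "40 subjects with poorly controlled asthma and 10 control subjects with no known lung disease", and "Participants with asthma then are randomized 1:1 to receive azithromycin, 250 mg, or placebo".

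Other parts of the plan keep variables continuous:

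- For diversity indices, "association with clinical and immune variables will be tested by regression analysis and generalized linear modeling" (same paragraph).
- "The Pearson correlation coefficient will be used to assess correlations among continuous variables" (Initial microbiome analysis).
- "Linear mixed effects models will be fit for continuous longitudinal outcomes" (Statistical analysis).
- Treatment effects on clinical outcomes are tested by t-tests on change from baseline to 8 weeks (Effect of treatment on clinical outcomes).

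**The concern.** ACT score, change in FEV1 and the inflammation markers are numeric. Cutting each into two classes before modelling treats patients just above and just below the cut as opposites, and patients far apart on the same side as equal.

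Two things are at stake. First, a sample of 40 facing about 300 candidate genera has little power to spare, and a split leaves at most 20 patients in the smaller class. Second, with no cut-point stated, the genera selected can depend on a choice made after the data are seen. The pilot is meant to inform the design of a larger trial, so efficient use of its data matters even though the step is exploratory.

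**Working it through.** **The plan's own figure.** The document gives no power or precision figure for these models. Its only power figure, under Power calculations, is for a paired change in *Pseudomonas* abundance with 20 patients and SD 1.8. The SD of change is 1.8 × √(2(1 − ρ)), that is 1.39 at ρ = 0.7 and 1.80 at ρ = 0.5. The exact paired t-test then gives detectable changes of 0.92 and 1.19, matching the stated 0.9 and 1.2. The figure reproduces but has no bearing on this point.

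**Inputs.** N = 40 asthma patients (Study Design) and about 300 genera (Microbial bioinformatics). Assumptions of this review: a normal outcome, a normal predictor, and the cuts shown below.

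**Information lost by a cut.** For a normal outcome and a small effect, the efficiency of a binary split relative to the continuous outcome is φ(c)² / [p(1 − p)]. Here p is the share on one side, c the matching normal quantile and φ the normal density.

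- Median split: 0.3989² / 0.25 = 0.637 = 2/π.
- 30/70: 0.3477² / 0.21 = 0.576.
- 20/80: 0.2800² / 0.16 = 0.490.

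| Split | Efficiency | Loss | 40 patients worth about |
|---|---|---|---|
| 50/50 | 0.637 | 36.3% | 25.5 |
| 40/60 | 0.622 | 37.8% | 24.9 |
| 30/70 | 0.576 | 42.4% | 23.0 |
| 20/80 | 0.490 | 51.0% | 19.6 |

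The median split is the best case under this model.

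**Power, single test, two-sided 5%, N = 40.** A median split shrinks a correlation r to r × √(2/π) = 0.798r. With Fisher's z at r = 0.40:

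- Continuous: atanh(0.40) × √37 = 2.577, and 2.577 − 1.960 = 0.617, giving 73%.
- Median split: atanh(0.319) × √37 = 2.012, and 2.012 − 1.960 = 0.052, giving 52%.

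Simulation (20,000 samples) gives 74% and 53%. At r = 0.45 it gives 85% and 64%.

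A separate simulation used the logit likelihood-ratio test itself (3,000 samples per setting). At r = 0.43, power is 81% continuous, 62% with a median split, 56% at 30/70 and 50% at 20/80. A median split needs about 60 patients to return to 80%. With no true association the logit test rejected in 5.0% to 5.9% of samples, so the split versions are not handicapped by a conservative test.

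**With about 300 genera.** At an illustrative threshold of 0.05/300, simulated power is:

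| True r | Continuous | Median split |
|---|---|---|
| 0.40 | about 11% | about 3% |
| 0.50 | about 32% | about 10% |

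With one true genus (r = 0.50) among 300 independent ones, that genus ranks first in 59% of samples with the continuous outcome and in 30% after a median split.

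**Dependence on the cut.** At r = 0.45, a median cut and a 30/70 cut give opposite significance verdicts in 28% of samples.

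**The case against.** The strongest case on the other side is about scope. A reader might infer that every genus-level predictive model in the plan rests on dichotomized outcomes. The documents do not support that:

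- Random Forest is planned for clinical outcomes, with no mention of cutting them.
- Pearson correlation could be applied to single genera.
- The closing part of Microbial bioinformatics compares changes in key genera with ACT, FEV1, methacholine responsiveness and cytokines, again with no mention of cutting.
- The sentence on LASSO and thresholding refers to generalized linear mixed models at large, which include a linear link.

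A reader might also infer that the main results are affected. They are not: the primary ACT and secondary FEV1 comparisons use continuous change.

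Three further objections have weight. ACT and FEV1 are not named in the sentence on dichotomizing; reading them in is an inference, though a fair one, because they stand in the aim of the same paragraph. The document does not say whether the models use one arm, all 40 asthma patients or all 50 subjects. The percentage loss is the same in each case, but the power figures are not. And the single-test power figures do not describe the planned multi-predictor selection, in which even the continuous version is weak.

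Finally, classification is a legitimate aim, and Power calculations calls the protocol exploratory. That limits the severity. It does not supply a cut-point or a reason for cutting a numeric outcome.

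**Conclusion.** The point holds for the taxa-based logit step only. That step dichotomizes clinical and immune outcomes without stating cut-points or a rationale. If, as seems likely, these are the numeric variables named in the same paragraph, the loss is at least about 36% of the information, and about 42% at a 30/70 cut.

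The 36% should not be read as a figure from the plan or as a fixed loss. It assumes a normal outcome, a small effect and a median split; skewed markers would first need a suitable transformation for it to apply. The fall in power from about 74% to 53% is a single-test illustration at N = 40 and r = 0.40. With about 300 genera both versions have far less power, but the continuous one stays ahead.

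No primary or secondary treatment comparison is affected. This is a cheap improvement, not a flaw that threatens the trial's conclusions.

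**What to change.** In Microbial bioinformatics, name the outcomes to be modelled. Fit the LASSO or thresholding models to each numeric outcome on its continuous scale as the main version, using a linear link within the generalized linear mixed model framework the plan already names. Keep logit models with ROC and the 0.632+ bootstrap for outcomes that are truly binary, or as a secondary display. For any dichotomized outcome that remains, state the cut-point and the reason for it before the data are examined. State also which subjects enter each model.

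The cost is a few sentences of text. Data and software are unchanged and only the outcome family differs. The downside is that ROC is no longer the headline summary, so a measure of prediction error suited to a continuous outcome would have to take its place.

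### The plan does not state the rows or resampling unit for the 0.632+ bootstrap and Random Forest; if single visit samples are drawn, an unrelated microbiome can look predictive

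*Combined protocol and SAP*

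**What the plan says.** Under Statistical analysis, Microbial bioinformatics, the plan states that "logit models will be generated using dichotomized clinical and immune variables as outcomes", with the microbiome data as predictors. The predictors are many: "Since we expect that the number of genera will be approximately equal to 300". LASSO or thresholding will reduce them "within the context of high-dimensional inference for generalized linear mixed effects models". The next sentence reads "Classification performance will be evaluated using ROC curve and the 0.632+ bootstrap method (68"). After that, "The machine learning approach, Random Forest, will also be applied to determine whether the microbiome is predictive of clinical outcomes".

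Study Design enrols "40 subjects with poorly controlled asthma and 10 control subjects with no known lung disease". After the baseline collection, "biological specimens (sputum, blood, FeNO) are collected again at 4 and 8 weeks", which makes three samples per subject. The Schedule of Events marks sputum induction and spirometry at four site visits. On either count the microbiome data are repeated within subject.

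The plan allows for clustering elsewhere: mixed models for longitudinal outcomes, and subjects as random effects in the Poisson models. It does not state which rows the classifiers use, whether the 0.632+ bootstrap draws samples or subjects, or how the Random Forest is validated.

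**The concern.** The 0.632+ bootstrap in its ordinary form and a Random Forest's built-in out-of-bag error both draw single rows and score the rows left out. On visit-level data, most left-out rows belong to people who also have rows in the training set. If a person's microbiome and clinical label both persist between visits, the model can recognise the person and return that person's label. The score then shows that a person's samples resemble each other. The plan asks something else: whether the microbiome predicts outcome in people the model has not seen.

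The safeguards in the text do not close this gap. A random effect governs inference within a fitted model and does not decide which rows are held out. A standard Random Forest has no subject term. Repeating variable selection inside each resample is right, but it does not remove a leak that comes from the resampling unit.

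The stake is the pilot's answer on prediction. Refining the informatics pipeline for the later trial is also one of the listed primary objectives, and the Poisson modeling paragraph promises an R package holding all the methods, so a leaking validation step could be carried forward.

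**Working it through.** **Plan's own figures.** The plan gives no AUC, error rate or sample size for the classifiers, so there is none to reproduce. The only within-subject correlation is in Power calculations: 0.5 or 0.7 for Pseudomonas abundance, with SD 1.8 and n = 20. The SD of change is 1.8 × √(2(1 − ρ)), which is 1.39 at ρ = 0.7 and 1.80 at ρ = 0.5. A paired t-test with 80% power then detects 0.92 and 1.19 (stated 0.9 and 1.2), with half-widths 0.65 and 0.84 (stated 0.7 and 0.84). Those figures reproduce after rounding. They confirm how the correlation is used and have no other bearing here.

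**Inputs.**
- From the documents: 40 asthma subjects; 3 visits (Study Design text) or 4 (Schedule of Events); about 300 genera.
- Assumed: correlation 0.5 to 0.7 for every genus, with 0.1 as a low case; Gaussian features; a median-split outcome whose latent variable has within-subject correlation between 0 and 1. The documents give no persistence for any dichotomized outcome.

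**Step 1: overlap between training and held-out subjects.** With V visits per subject and row-wise draws, the chance that a held-out row's subject also appears in the training draw is about 1 − exp(−(V − 1)).
- V = 3: 1 − exp(−2) = 0.865; simulated 0.866.
- V = 4: 1 − exp(−3) = 0.950; simulated 0.951.

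**Step 2: why 0.632+ does not correct this.** Let err be the training error, e the out-of-bag error and γ the no-information error. Then R = (e − err)/(γ − err), w = 0.632/(1 − 0.368R), and the estimate is (1 − w)err + w·e. If e is honest and the predictors are useless, e = γ, so R = 1, w = 0.632/0.632 = 1, and the estimate is γ, which is chance. If leakage lowers e, then R falls and the estimate falls with it. The correction relies on e being honest.

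**Step 3: null simulation.** 40 subjects, 3 visits, 300 features unrelated to outcome; 25 data sets for the L1 logit, 12 for Random Forest, 12 bootstrap draws each. Cells show AUC / 0.632+ error.

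| Classifier | Genus correlation | Latent outcome correlation | Rows drawn | Subjects drawn |
|---|---|---|---|---|
| L1 logit | 0.5 | 0.5 | 0.61 / 0.39 | 0.51 / 0.47 |
| L1 logit | 0.7 | 0.7 | 0.71 / 0.29 | 0.51 / 0.47 |
| L1 logit | 0.5 | 1 (constant label) | 0.84 / 0.18 | 0.49 / 0.47 |
| L1 logit | 0.7 | 1 | 0.92 / 0.10 | 0.54 / 0.45 |
| L1 logit | 0.1 | 1 | 0.57 / 0.43 | 0.50 / 0.47 |
| L1 logit | 0.5 | 0 | 0.50 / 0.48 | 0.49 / 0.48 |
| L1 logit, one row per subject | – | – | 0.47 / 0.48 | – |
| Random Forest | 0.5 | 1 | 0.83 / 0.22 | 0.48 / 0.49 |
| Random Forest | 0.7 | 1 | 0.94 / 0.12 | 0.53 / 0.48 |

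Monte Carlo standard errors of the AUC are 0.005 to 0.022. A separate L1-logit simulation with equal genus and outcome correlations gave row-wise AUC 0.64 to 0.74 at four visits and 0.57 to 0.64 at two, and 0.50 with whole-subject draws.

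**Step 4: plausibility.** For a median split, two visits of one subject share a label with probability 1/2 + arcsin(ρ)/π, which is 0.67 at ρ = 0.5 and 0.75 at ρ = 0.7. A rule that only recognised the subject and returned the label from one other visit would be right that often. The row-wise accuracies of 1 − 0.39 = 0.61 and 1 − 0.29 = 0.71 sit just below these values, as the mechanism predicts.

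**The case against.** The strongest objection is that the plan nowhere says rows are drawn. A reader might infer from the named methods that samples rather than subjects will be resampled. The documents do not support that as a statement of fact: unit and rows are both left open. One row per subject is a fair reading too, since Outcome Measures defines most endpoints as change from baseline to 8 weeks and the bioinformatics text lists changes in FEV1 among its targets. That part of the objection stands, and the point is conditional on it. On the other side, placing the selection step in mixed-effects models makes little sense without repeated rows, so visit-level data are a natural reading for the logit models. For the Random Forest the text gives no such pointer.

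Second, the bias needs three things together: visit-level rows, persistent genera and a persistent label. That stands. A reader might infer that the prediction analysis would come out positive under the null; the one-row and non-persistent cases above show that this does not follow in general. A constant label is nonetheless easy to produce. The Schedule of Events marks ACT and serum IgE at Visit 1 only (although the Study Design text repeats ACT at 4 and 8 weeks), and joining such a label to samples from every visit creates that case.

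Third, the correlation of 0.5 to 0.7 is a conditional power input for one genus. Applying it to 300 genera, and to the outcome, is an assumption.

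Fourth, the consequence is limited. The protocol calls itself exploratory, classifier performance is neither a primary nor a secondary outcome, and power for the later trial is to come from the Poisson and multivariate regression models. This stands, and it limits how much weight the point carries.

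**Conclusion.** The concern holds in conditional form. The plan names validation methods whose ordinary implementations draw rows, applies them to data collected repeatedly from the same people, and fixes neither the rows nor the resampling unit. If visit-level rows are drawn, an unrelated microbiome gives an AUC of roughly 0.6 to 0.75 when genera and outcome have within-subject correlation 0.5 to 0.7, and 0.83 to 0.94 in the simulated constant-label cases with the same genus correlations. Whole-subject draws bring this back to 0.48 to 0.54. There is no bias with one row per subject or with a label that does not persist, and it is small when genera persist little (0.57 at correlation 0.1).

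These sizes rest on Gaussian features, a common correlation across genera and an assumed outcome persistence; the Random Forest figures come from few data sets. No false-positive rate can be attached to the plan, because it specifies no test of AUC against chance and no success threshold. The comparison of ACT change between arms is untouched.

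**What to change.** In Microbial bioinformatics, state which rows enter each classifier and choose one of two routes.

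- **Visit-level rows:** the subject is the resampling unit for the 0.632+ bootstrap and for any Random Forest error estimate. All visits of a subject are drawn or held out together, only wholly undrawn subjects are scored, variable selection is repeated inside each draw, and the default out-of-bag error is not reported.
- **One row per subject**, such as a single visit or one change score. The leak then does not arise, though selection must still be repeated inside each draw.

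If an AUC is to be tested against chance, use a null that permutes whole subjects' outcome series across subjects. A test that treats visits as independent ignores the clustering even when the draws are by subject.

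The cost is one or two sentences and a grouped-resampling option in the code, with no change to data collection. The downside is that reported AUCs will be lower and more variable.
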